4.7 Instructions for Patients who Do Not Start Assigned Protocol Treatment

If a patient does not receive any assigned protocol treatment, baseline and follow-up data will still be collected and must be submitted through Medidata Rave according to the schedule in the EA5161 Forms Completion Guidelines.

Rev. Add3 **5. Treatment Plan**

Rev. Add4 **5.1 Agent Administration**

Treatment will be administered on an outpatient basis unless local institutional standard practice requires inpatient administration. No therapies (investigational or commercial agents) other than those described below may be administered with the intent to treat the patient's malignancy. Reported adverse events and potential risks for nivolumab, cisplatin or carboplatin, and etoposide are described in Sections [5.3](#) and [8](#). Appropriate dose modifications are described in Section [5.4](#). BSA should be recalculated if $\geq 10\%$ weight loss.

Cycle Length (Cycles 1-4) = 3 weeks (21 days)

Maintenance Cycle Length (Cycles 5+) = 6 weeks (42 days)

NOTE: All treatment visits must occur $+$ / $-$ 3 days from the scheduled date unless otherwise noted. If scheduled dosing and study assessments are precluded because of a holiday, weekend, or other event, then dosing may be postponed to the soonest following date, with subsequent dosing continuing on a 21-day schedule during Cycles 1-4 or every 2 weeks during maintenance nivolumab. If treatment was postponed for fewer than 3 days, the patient can resume the original schedule.

Arm A Description (Nivolumab arm) Cycles 1-4***					
Agent	Pre-medications**; Precautions	Dose	Route	Schedule	Cycle Length
Nivolumab ****		360 mg IV over 30 minutes	IV	Day 1	21 days (3 weeks)
Carboplatin*	Dexamethasone 5-HT3 antagonist Aprepitant or Fosaprepitant	AUC 5 or 6 IV over 30 to 60 minutes	IV	Day 1 after nivolumab infusion is completed	
Cisplatin*	Dexamethasone 5-HT3 antagonist Aprepitant or Fosaprepitant	75mg/m ² IV over 60 to 120 minutes	IV	Day 1 after nivolumab infusion is completed	
Etoposide	Dexamethasone 5-HT3 antagonist	100 mg/m ² IV over 60 to 120 minutes	IV	Days 1, 2, 3 after platinum infusion is completed	

Nivolumab is given first, followed by carboplatin/cisplatin, then etoposide.

* The decision to administer cisplatin or carboplatin is at the discretion of the treating physician. If the choice is made to administer carboplatin, starting dose of AUC 5 or 6 is at the discretion of the treating physician.

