7.1 Therapeutic Parameters

1. Pre- study screening CT scans and MRIs used to assess all measurable or non-measurable sites of disease must be done within 4 weeks prior to randomization/registration.
2. Pre-study screening CBC (with differential and platelet count) and chemistries as outlined in Section [3.1](#) should be done \leq 1 week before randomization/registration. All other pre-study screening labs should be done within 2 weeks prior to randomization/registration. Screening assessments performed \leq 72 hours before Cycle 1, Day 1 are not required to be repeated for Cycle 1, Day 1.
3. Please see Section [5.1](#) for more information on treatment administration parameters.

Therapeutic parameters	Pre-study screening	Cycle 1 Day 1	Cycle 2 Day 1	Cycle 3 Day 1	Cycle 4 Day 1	Maintenance Nivolumab Cycle 5+ Day 1, 15, 29	Observation (Arm B) ¹¹	Post Treatment/Observation ¹² to 5 years from study entry
Full Medical History	X							
Interval History ¹		X	X	X	X	X	X	X
Vital signs including weight ¹	X	X	X	X	X	X	X	X
Performance status ¹	X	X	X	X	X	X	X	X
CBC with Differential ²	X	X	X	X	X	X	X ¹¹	
Serum chemistry ²	X	X	X	X	X	X	X ¹¹	
TSH, reflex free T3, reflex free T4 ³	X	X		X		X ³		
Amylase ⁴		X						
Lipase ⁴		X						
HIV, HBV, HCV serology ⁵	X							
Pregnancy Test ⁶	X							
EKG ⁷	X							
Urinalysis ⁸	X	X	X	X	X	X ⁸		
CT chest ⁹	X			X		X	X	X
CT abdomen ⁹	X			X		X	X	X
CT pelvis ⁹	X			X		X	X	X
MRI brain ¹⁰	X							

1. At subsequent visits, symptom-directed history and physical examinations including vital signs, weight and performance status should be performed. Symptom-directed history, physical exam and performance status may be performed up to 72 hours prior to each cycle.
2. CBCs (with differential and platelet count) which includes WBC, ANC, Platelets, Hgb, and Hct, and chemistry to include Albumin, alkaline phosphatase, total bilirubin, carbon dioxide, BUN, calcium, chloride, creatinine, glucose, LDH, phosphorus, potassium, total protein, SGOT [AST], SGPT [ALT], sodium, required for protocol therapy must be done \leq 72 hours prior to treatment administration. Magnesium is only required for patients receiving cisplatin on day 1 of each cycle that cisplatin is administered. For cycle 1 day 1, need not be repeated if the screening labs were done within 72 hours of treatment administration.

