3. TSH, reflex free T3 and reflex free T4 will be done at screening as clinically indicated. For the Nivolumab Arm only, these tests will also be done on C1D1, C3D1, C5D1, and every 8 weeks during the maintenance phase. Thyroid labs collected at screening do not need to be repeated at C1D1 if done within 72 hours of treatment administration.
4. Amylase, lipase will be required for patients receiving nivolumab on C1D1 and when clinically indicated.
5. All patients will be tested for HIV, hepatitis B and hepatitis C at screening, if clinically indicated.
6. Blood or Urine pregnancy test (women of childbearing potential). All women of childbearing potential must have a negative pregnancy test (sensitivity of at least 50 mIU/mL). The pregnancy test must be performed within 14 days prior to registration.
7. All patients will have an EKG at screening, if clinically indicated. Patients randomized to the Nivolumab Arm will have troponin as clinically indicated. Further cardiac evaluation is recommended including troponin, EKG, echocardiogram, and cardiology consult when clinically indicated.
8. Urinalysis will be required at screening for all patients and on day 1 of every cycle on the Nivolumab Arm. It does not need to be performed on days 15 or 29 for Cycle 5+.
9. Screening assessments will include CT chest and abdomen. CT pelvis should be performed as clinically indicated. On study and follow-up assessments will include a CT chest and abdomen at each time point, and CT pelvis as clinically indicated. For both Arm A and Arm B, all patients will be evaluated for response while on study using radiographic evaluations with tumor measurements every 6 weeks (+/- 7 days) for the first 6 months on study, every 8 weeks (+/- 7 days) until 1 year on study, and then every 12 weeks (+/- 7 days) after 1 year on study until the patient discontinues protocol treatment (Arm A) or the end of observation (Arm B) and enters follow-up (see footnote 12 for follow-up schedule). Documentation (radiologic) must be provided for patients removed from study for progressive disease. For all patients on Arm A and Arm B, CT scans will be done until disease progression.
10. Head CT allowed, if patient cannot tolerate MRI. Brain imaging will be done at screening and then as clinically indicated.

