11. For Arm B patients on observation, symptom-directed history and physical examinations including vital signs, weight and performance status should be performed every 6 weeks (+/- 7 days) for the first 6 months on study, then every 8 weeks (+/- 7 days) until 1 year on study; and every 12 weeks (+/- 7 days) after 1 year on study, alongside the radiologic evaluations. Labs (CBC w/diff, serum chemistries) are done as clinically indicated. CT scans will be done until disease progression
12. Follow-up after patient discontinues protocol treatment (Arm A) or the end of observation (Arm B): every 3 months for patients < 2 years from registration, every 6 months if patient is 2-3 years from registration, and yearly until 5 years from registration. Patients in the observation phase on Arm B may be seen more frequently per schedule of CT scans as per footnote 9. All patients, including those who discontinue protocol therapy early, will be followed for response until progression, even if non-protocol therapy is initiated, and for survival for 5 years from the date of registration. For all patients during follow-up, symptom-directed history and physical examinations including vital signs, weight and performance status should be performed until progression. Follow-up for survival after progression may occur via phone calls.

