8.3.11 Nursing/Patient Implications

- 8.3.11.1 Monitor CBC and platelet count; nadir occurs at approximately day 21 with recovery by day 28-30.
- 8.3.11.2 Premedicate with antiemetics—evaluate effectiveness. Ondansetron (or other 5HT3 antagonist) and dexamethasone are required.
- 8.3.11.3 Monitor fluid status—maintain adequate hydration. Pre- and post-treatment hydration may be administered per institutional standards.
- 8.3.11.4 Assess skin/mucous membranes.
- 8.3.11.5 Assess for signs of peripheral neuropathy—coordination, sensory loss.

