9.3 Statistical Analysis Plan

The primary and some secondary analyses will include all eligible and treated patients. Exception to this include: analysis of toxicity data, which will include all patients who received study drug regardless of eligibility, and analyses of response, which will include eligible and treated patients with measurable disease. Time-to-event data, such as PFS and OS, will be estimated using the Kaplan-Meier method, and Cox proportional hazards models will be used to estimate the treatment hazard ratios. The primary comparison of PFS will use a logrank test stratified on the randomization stratification factors with a one-sided type I error rate of 10%. Other comparisons of groups will be made using the log rank test and Cox modeling. Categorical data, such as response rates (CR+PR) and toxicity, will be compared using Fisher's exact tests with a one-sided type I error rate of 10%; multivariable logistic regression modeling will be used to adjust for the effect of any covariates that are associated with these categorical outcomes. Continuous outcomes will be analyzed using Wilcoxon rank sum test, and multivariable linear regression models may be used to adjust for multiple associations with outcome.

Modeling procedures will implement backward selection; variables significant at the 0.10 level in the univariate setting will be chosen for inclusion in an initial full model, and at each step the least significant variable will be removed from the model. Only those covariates with $p < 0.05$ will remain in any final models, unless there are factors identified by the study team as crucial to model interpretation.

Point estimates of all endpoints will be accompanied by the corresponding 95% confidence intervals; however, 80% confidence intervals will also be provided for

the primary endpoint (PFS) hazard ratio. In the event that there are missing data, no imputation of the missing data will be conducted. We will assume that data are missing at random and will conduct all analyses as originally planned because we do not anticipate an excess of missing data.

Subset analyses are planned for all stratification factors and all known prognostic factors, such as performance status, age, sites of metastases, gender, etc. Subset analyses of all variables, including correlatives, are considered to be exploratory in nature.

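### Section 9.3 sets no common at-risk period for toxicity, so its Fisher test contrasts whole regimens and cannot by itself show whether nivolumab adds toxicity to chemotherapy

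*Combined protocol and SAP*

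**What the plan says.** Toxicity is a secondary endpoint (Section 2.2.3), and the hypothesis in Section 1.4 is that the combination improves PFS without raising toxicity. Section 9.2 defines toxicity by CTCAE alone. Section 9.1 speaks of toxicity with first-line therapy but gives no end to the period.

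Section 9.3 states: "Categorical data, such as response rates (CR+PR) and toxicity, will be compared using" Fisher's exact test at a one-sided 10% level. The analysis set is given in "analysis of toxicity data, which will include all patients who received study drug regardless of eligibility". A logistic model may adjust for associated covariates, but exposure time is not mentioned. The direction of the test is not stated, nor whether events are all-cause or attributed.

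The treatment and testing schedules differ by arm after cycle 4:

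- **Arm A:** Section 5.1 describes visits "with subsequent dosing continuing on a 21-day schedule during Cycles 1-4 or every 2 weeks during maintenance nivolumab", for up to 2 years. Section 7.1 marks blood count and chemistry under "Maintenance Nivolumab Cycle 5+ Day 1, 15, 29". Thyroid tests follow an Arm A schedule: "For the Nivolumab Arm only, these tests will also be done on C1D1, C3D1, C5D1, and every 8 weeks during the maintenance phase". On-treatment urinalysis is also scheduled in Arm A only.
- **Arm B:** at most four cycles, then observation. Section 7.1 footnote 11 schedules a history and examination every 6 weeks in the first 6 months, then every 8 and every 12 weeks. For blood tests it says "Labs (CBC w/diff, serum chemistries) are done as clinically indicated".

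Section 5.2.3 leaves the timing of routine adverse-event reporting to the forms packet, which is not among the documents. The 30-day limits elsewhere in Section 5.2 govern expedited reporting.

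**The concern.** A proportion of patients ever having an event rises with time at risk and with the number of tests. Both are larger in Arm A by design. An excess in Arm A could therefore mean that nivolumab makes chemotherapy more toxic, that patients were treated for longer, or that they were tested more often. The planned test gives one answer for all three.

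This matters because Section 1.4 presents the trial as groundwork for a phase III study and hypothesises no added toxicity. A reader planning that study would want to know what nivolumab adds during chemotherapy and, separately, what maintenance costs.

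**Working it through.** The plan states no figure for the toxicity comparison, so there is none to reproduce. Its PFS inputs do reproduce: ln 2/5 = 0.139 and ln 2/8 = 0.087 per month, as in Section 9.4.

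**Inputs from the documents.** 150/2 = 75 per arm (9.4, assuming all are treated). Chemotherapy lasts 4 x 21 = 84 days = 2.76 months (5.1). Nivolumab is capped at 24 months (5.1). Median PFS is 8 against 5 months (9.4).

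**Assumptions.** Nivolumab causes no toxicity. 60% of patients would have a first event over a full 84 days, so the rate is h = -ln(0.4)/2.76 = 0.332 per month. After that, r = 1-3% per month in both arms. PFS is exponential. The test looks for a higher rate in Arm A. A tail of 30 days is 0.99 month.

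**Step 1, time on treatment.** The mean of min(PFS, c) is (1 - exp(-λc))/λ.
- Arm A: (1 - exp(-0.0866 x 24))/0.0866 = 10.1 months.
- Arm B: (1 - exp(-0.1386 x 2.76))/0.1386 = 2.3 months.

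**Step 2, true size.** Exact enumeration of the one-sided 10% Fisher test with 60% in both arms gives 7.8%.

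**Step 3, the planned whole-study test.** P(event) = 1 - E[exp(-H(u))], where H(u) = h x min(u, 2.76) + r x max(u - 2.76, 0) and u is the time observed. In Arm A, u = min(PFS, 24) + 0.99. In Arm B, u = PFS + 0.99, or min(PFS, 2.76) + 0.99 if collection ends 30 days after chemotherapy.

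| r per month | Arm A | Arm B, to progression + 30 d | Rejects | Arm B, to chemotherapy + 30 d | Rejects |
|---|---|---|---|---|---|
| 1% | 61.0% | 58.8% | 12.7% | 57.0% | 18.1% |
| 2% | 63.7% | 60.6% | 14.8% | 57.3% | 27.0% |
| 3% | 66.0% | 62.3% | 16.8% | 57.6% | 36.0% |

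With median PFS 5 months in both arms, the test rejects in 7.4-7.8% under the first window (no inflation) and 11.7-19.9% under the second. With PFS back at 8 against 5 months, a base rate of 30% gives 13-22% and 24-61%, and a base rate of 80% gives 11-13% and 14-23%.

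**Step 4, a common window ending at day 84 (base 60%, 8 against 5 months).**
- Observed to progression + 30 days, u = min(PFS + 0.99, 2.76): 57.9% against 56.7%, rejects in 10.4%.
- Collection stops at progression itself: 54.3% against 51.3%, rejects in 15.4%. The whole-study test under that same rule rejects in 18.4-23.8%.
- All patients followed to day 84: 60% in each arm, rejects in 7.8%.

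**Step 5, blood tests around cycle 4.** Section 7.1 ties these to dosing: tests "required for protocol therapy must be done" within 72 hours before treatment. Both arms therefore have scheduled counts after cycles 1, 2 and 3. After cycle 4 only Arm A has one, on cycle 5 day 1 (about day 85). Section 8.3.11 says of carboplatin that the "nadir occurs at approximately day 21 with recovery by day 28-30". Arm B does have a week-12 visit (about day 84), with blood tests only if indicated. Suppose each scheduled draw independently shows an abnormality with probability p (assumed), and a share f of Arm B's cycle 4 abnormalities is found anyway. Arm A records 1 - (1-p)^4 and Arm B records 1 - (1-p)^3 x (1 - fp).

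| p | Arm A | Arm B, f = 0 | Rejects, f = 0 | f = 50% | f = 75% |
|---|---|---|---|---|---|
| 5% | 18.5% | 14.3% | 21% | 12% | 9% |
| 10% | 34.4% | 27.1% | 31% | 16% | 11% |
| 20% | 59.0% | 48.8% | 45% | 22% | 14% |

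**The case against.** Maintenance is part of the assigned Arm A regimen, so events during it belong in an Arm A total, and the Fisher test is a valid comparison of the regimens as given. The stated objective is to evaluate a toxicity profile. The distortion works against the trial's hypothesis, so it would not produce false reassurance. All of this stands. It limits the harm, but the test still cannot address the specific hypothesis in Section 1.4.

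A reader might infer that the test is invalid, or that it is nearly certain to report excess toxicity. The documents do not support either.

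- A model with one constant event rate throughout, and Arm B observed only to 30 days after chemotherapy, rejects in 54-99% of trials at rates of 1-10% per month. But it gives chemotherapy no more toxicity per month than maintenance, and no section states that Arm B window.
- Section 5.2.12 refers to a late adverse event form and a post-registration folder, so recording after treatment exists in some form.
- The 45% figure in step 5 requires that Arm B's week-12 visit finds no cycle 4 abnormality at all. The carboplatin nadir also says nothing about patients given cisplatin.
- The model ignores stopping nivolumab for toxicity and the 25-month study duration. Both would shorten Arm A exposure.

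It could also be said that a cycle 1-4 comparison is no better. Under matched assumptions it is: 10% against 13-17%, or 15% against 18-24% if collection stops at progression.

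The silence on test direction, attribution and collection window is missing detail, not a flaw in method.

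**Conclusion.** The point holds in limited form. Section 9.3 compares ever/never toxicity between arms with very different treatment durations and testing schedules, and sets no common period. The result describes the whole regimens and cannot by itself show whether nivolumab adds toxicity to chemotherapy.

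The direction, towards more recorded toxicity in Arm A, follows from the schedules. The size does not: event rates are assumed and the collection window is unseen. The effect of longer treatment ranges from nil (both arms observed to progression, equal PFS) to rejection in 13-17% or 18-36% of trials in the base case, against a true size of about 8%. The missing cycle 4 draw adds little if Arm B's week-12 visit catches most abnormalities.

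Toxicity is secondary. The PFS analysis, the sample size and the interim rule are untouched.

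**What to change.** Amend Section 9.3 as follows.

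1. Keep the whole-study toxicity table and test, labelled as a whole-regimen contrast with its direction stated, so that late immune events stay visible.
2. Add a between-arm comparison of worst grade over cycles 1-4, ending before the first cycle 5 dose in Arm A and at the matching time in Arm B (about day 84). Count events whether or not the patient progressed or stopped early, where data allow. Give the risk difference with a 95% confidence interval.
3. Report toxicity after cycle 4 separately by arm, as exposure-adjusted rates or time to first event, noting the different test schedules.
4. Flag laboratory events found only by tests scheduled in Arm A: thyroid, urinalysis and the cycle 5 day 1 pre-dose draw.
5. State, or cross-refer to, the adverse-event collection window for each arm, and say whether events are all-cause or attributed.

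The cost is SAP wording and one or two extra tables, with no change to treatment, visits or sample size. The forms packet should be checked to confirm that routine events carry a cycle or onset date. Section 5.2.4 files forms by treatment cycle, but it is written for expedited events.

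There are two downsides. The cycle 1-4 comparison omits late immune events, which is why the whole-study table stays. Some imbalance also remains if collection stops at progression and PFS differs: about 3 percentage points (54.3% against 51.3%) in the base case.

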9.4 Sample Size Considerations

The primary comparison will include all eligible and treated patients, of whom 135 will be accrued and randomized equally, for a total accrual of 67 patients per arm. After adjusting for an ineligibility rate of 10%, the total required sample size for randomization is 150 patients. Using an overall one-sided 0.10 level log rank test, this study will have 88% power to detect a 37.5% reduction in the PFS hazard rate of 0.139 to 0.087 based on the estimated accrual and follow-up period. Assuming an exponential survival, this corresponds to a 60% improvement in the median PFS of 5 months on CE to 8 months on CE plus nivolumab. The number of PFS events needed to achieve this power is 113 events under the alternative hypothesis.

Correlative Study Statistical Considerations:

Tumor DNA levels obtained from the serial collection of cfDNA samples will be examined to explore whether clinical outcome is associated with fluctuations in DNA levels following the administration of therapy. Plasma will be collected from 30 patients on each arm of the study at baseline and cycle 2 day 1.

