9.6 Randomization Scheme

Randomization to treatment will be determined using permuted blocks within strata with dynamic balancing on main ECOG-ACRIN institutions plus affiliates. The randomization will be stratified by gender (Male vs. Female) and LDH (WNL vs. > upper limit of normal).

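### Response and toxicity go to an unstratified, conservative Fisher's test, and the randomisation factors are not fixed in any secondary comparison; a wording change in 9.3 recovers several points of power

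*Combined protocol and SAP*

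**What the plan says.** Section 9.6 sets the randomisation factors: "The randomization will be stratified by gender (Male vs. Female) and LDH". Section 9.3 carries them into one analysis only, the PFS comparison, which uses "a logrank test stratified on the randomization stratification factors".

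The other comparisons in 9.3 are worded differently:

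- **Response and toxicity:** Fisher's "exact tests with a one-sided type I error rate of 10" per cent, with no mention of strata. The same sentence adds that "multivariable logistic regression modeling will be used to adjust for the effect of any covariates that are associated with these categorical outcomes".
- **Model building:** covariates are screened at 0.10 one at a time, then removed backwards until only those with p < 0.05 remain, "unless there are factors identified by the study team as crucial to model interpretation". No such factor is named.
- **OS:** "Other comparisons of groups will be made using the log rank test and Cox modeling".

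Section 9.4 plans for eligible and treated patients, "of whom 135 will be accrued and randomized equally, for a total accrual of 67 patients per arm", out of 150 randomised. Section 9.1 lists OS, response and toxicity as secondary objectives of estimation. No target difference and no power is given for the between-arm response test.

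**The concern.** Two separate things are worth a look.

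First, the randomisation factors are used in one analysis and left open in the rest. Whether sex and LDH enter the response and toxicity models depends on p-values in the trial's own data, so the adjusted analysis is not fixed in advance.

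Second, Fisher's test is discrete. With about 67 patients per arm it cannot use all of a one-sided 10% level. The unused level is lost power, both for seeing a response improvement and for seeing excess toxicity. Section 1.4 puts forward a PFS benefit with no added toxicity as the trial's hypothesis, so a toxicity test that rarely rejects has some bearing on how the results are read.

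**Working it through.** **Inputs.** From 9.4: 135 analysed patients. They do not split evenly, so I used 67/67, 67/68 and 68/67. For toxicity, 9.3 includes everyone who received study drug, so up to 75 per arm. Response is restricted to measurable disease, but 3.1.3 requires that of everyone. Section 1.1 gives a control response of 50-70%. The size of the response difference and the prognostic strength of sex and LDH are not in the documents; the values below are assumptions.

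**Method.** With a control responders out of n1 and b experimental responders out of n2, the one-sided Fisher p-value is P(X ≥ b), where X is hypergeometric (n1+n2 patients, a+b responders, n2 drawn). The probability of rejection is the sum over all (a, b) with p ≤ 0.10 of Bin(a; n1, π1) × Bin(b; n2, π2). Setting π1 = π2 gives the attained level; otherwise the sum is power.

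**Step 1: the plan's own Fisher figure.** Section 9.4 states 85% power for the cfDNA analysis (60 patients split at the median, 40% vs 80%, one-sided 0.025). Enumeration at 30/30 gives 85.1%. The uncorrected normal formula gives Φ[(0.4√30 − 1.960√(2×0.6×0.4)) / √(0.24+0.16)] = Φ(1.317) = 90.6%. The stated figure reproduces and already allows for Fisher's conservatism.

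**Step 2: attained level at nominal 10%.**

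| Setting | True rate | Fisher level |
|---|---|---|
| Response, 67/67 | 50-80% | 6.8-7.4% |
| Response, 67/68 or 68/67 | 50-80% | 6.8-8.4% |
| Response, 75/75 | 50-80% | 6.8-8.3% |
| Toxicity, 67/67 | 2%, 5%, 10% | 1.3%, 3.9%, 5.6% |
| Toxicity, 75/75 | 2%, 5%, 10% | 1.6%, 4.3%, 5.9% |

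**Step 3: power for response at 67/67.** The score test is the uncorrected chi-square. Boschloo's test orders tables by the Fisher p-value and raises the cut-off until the worst-case level reaches 10%; here its maximum level is 9.9%.

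| Control vs experimental | Fisher | Score | Boschloo |
|---|---|---|---|
| 50% vs 60% | 37.8% | 44.6% | 44.6% |
| 70% vs 80% | 44.7% | 52.3% | 51.7% |
| 60% vs 75% | 65.9% | 72.0% | 71.1% |
| 60% vs 80% | 86.8% | 90.3% | 89.9% |

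At 67-68 per arm the gap between score and Fisher is 6.7-8.6 points for a 10-point difference and 5.9-6.9 for 15 points (control 50-70%). For 20 points it is 3.5-4.3 (control 50-60%).

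Boschloo gains 3.1-7.0 points over Fisher in the 67/67 table. The gain is not stable across allocations: at 67/68, for 50% vs 60%, Fisher has 41.8% and Boschloo 41.9%. Over 67/68 and 75/75 it ranges from about 0 to about 6 points.

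**Step 4: how much of this is stratification.** Assume control response 60%, treatment odds ratio 2.0 and LDH odds ratio 2.5. Simulated power is Fisher 63.2%, unstratified chi-square 69.7%, stratified CMH 71.4%. Discreteness accounts for 69.7 − 63.2 = 6.5 points and stratification for 71.4 − 69.7 = 1.7.

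A wider simulation (200,000 runs per setting, four equal strata, 68 per arm) gives these gains of CMH over unstratified chi-square:

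| Assumed odds ratios, sex / LDH | Gain (points) |
|---|---|
| 1.0 / 1.0 | about 0 |
| 1.5 / 1.5 | 0.1-0.4 |
| 1.5 / 2.0 | 0.3-1.0 |
| 2.0 / 3.0 | 0.7-2.4 |

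CMH's attained level was 9.5-10.3% in these runs and up to 10.7% in a 20,000-run simulation. With a continuity correction, CMH falls back to about Fisher's performance when the strata are not prognostic: 65.9% against 66.6% for 60% vs 75%.

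**Step 5: OS.** Assume a 10-month median, HR 0.70 and LDH HR 1.8-2.2. The unstratified log-rank test has 59-62% power and the stratified test 62-64%.

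**The case against.** The strongest reply is that nothing in 9.3 is wrong, and much of that stands.

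- **Level.** A reader might infer that the test breaks its stated error rate. It does not. For an exact test 10% is a ceiling, and Fisher stays below it.
- **Cause.** A reader might infer that leaving out sex and LDH causes the power loss. Step 4 shows that it does not: discreteness causes most of it.
- **Strata ignored.** A reader might infer that the plan disregards the factors altogether. It plans adjusted logistic regression, allows crucial factors to be kept, and lists subset analyses for the stratification factors. A strongly prognostic LDH might well be selected. What remains is that neither factor is named as a forced term.
- **Underpowered response endpoint.** The documents claim no response power and no target difference, so no stated figure fails. Where the plan does claim power for Fisher's test, its figure is right.
- **Comparator.** Part of the score test's advantage is extra level: it reaches 11.4% at 67/68 with 50% response, and about 12% at a 2% event rate. An unconditional exact test ordered by the pooled z statistic recovers only 0-3 points over Fisher at 67-68 per arm. Boschloo's test answers this in part, since it holds 10% and still gains 3-7 points at 67/67, but less and less evenly at other sizes.
- **OS.** The gain is small, the ranges touch, and the inputs are assumed. The wording does not exclude strata.

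The reply does not remove the two residual points: an avoidable loss of power, and adjusted analyses that are left to data-driven selection.

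**Conclusion.** The point holds as a matter of efficiency and pre-specification in secondary analyses, not as an error. Fisher's test at nominal one-sided 10% attains about 7-8% for response and about 1-6% for toxicities with true rates of 2-10%. Against a score or CMH test this costs about 6-9 points of power for response differences of 10-15 points and about 3-4 for 20. Under strict 10% control, Boschloo's test recovers about 3-7 points at 67/67 and about 0-6 at 67/68 or 75/75.

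Stratifying contributes about 0-2 points. The case for it rests mainly on consistency with the randomisation and on fixing the analysis in advance. The primary PFS analysis and its power are untouched.

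The attained levels need only the plan's sample sizes and a range of event rates. The power gaps rest on assumed response differences, and the stratification and OS gains also on assumed prognostic effects.

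**What to change.** In section 9.3:

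1. Compare response, and the binary toxicity endpoint that the team names as its main one, with a CMH test stratified by sex and LDH at one-sided 10%, without continuity correction. Report a stratified risk difference with its confidence interval.
2. Use Boschloo's test instead where strict 10% control is wanted or events are sparse.
3. Keep sex and LDH in the response and toxicity logistic models whatever their p-values; apply backward selection only to other covariates.
4. Stratify the OS log-rank test and Cox model by the same two factors.

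The cost is SAP wording; no patients or data are added. The downside is that CMH is a large-sample test whose level may sit slightly above 10% (up to about 10.7% in simulation).
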